
Overall alpha will control for type 1 error at a rate of 5% using the Hochberg correction. If one endpoint is below the 2.5% level or if both endpoints are below the 5% level of significance the study is declared a success.
 
The sample size for the study was calculated assuming an estimate of the effect size between active treatment and placebo of 0.51 on both endpoints..
 
For the secondary efficacy analysis, the same MMRM as for the primary analysis will be calculated without a formal confirmatory significance test. At each visit, estimates for the adjusted changes from baseline in both the treatment and the placebo arm (adjusted for individual differences and differences in baseline and therapy status) as well as for the difference in changes between the two arms will be presented, including 95% confidence intervals (CI).
 
An interim analysis will be performed after 90 participants have completed the specific week assessments (expected 108 patients enrolled after accounting for 20% dropout). Individuals that had the opportunity to complete their specific week visit, but were lost to follow-up, will also be included in the analysis, however, will not be included in the 90-patient count required for initiation of the interim analysis. The objective of this interim analysis will be to reassess the sample size based on the observed variability and effect sizes. If the conditional power is too low for both endpoints or the required sample size adjustment is considered to be too large, the study sample size will not be adjusted.
 
Details of the planned analyses will be provided in the SAP which will be finalized prior to conduct of the interim analysis.
	
STUDY PERIOD 
 - First patient in (FPI) is planned on Q1-2021 - Last patient in (LPI) is planned on Q3-2023 - Last patient out (LPO) is planned on Q4-2023 	

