4.2. Removal of Participants from Therapy or Assessment

Participants are free to discontinue trial participation at any time. Withdrawal from the trial will not affect or prejudice participants further care or treatment. In addition, participants may be withdrawn from study treatment and assessments at any time, if deemed necessary by the PI or Sponsor.

Potential reasons for withdrawal of participants from this study include, but are not limited to:

- The participant withdraws his or her consent (defined as a participant who explicitly takes back his or her consent)
- The PI considers it, for safety and/or study compliance reasons, in the best interests of the participant that he or she be withdrawn
- Initiation of concomitant medication prohibited by the study protocol (see [Table 2](#))
- Initiation of psychotherapy in psychotherapy naïve participants at baseline
- Discontinuation of psychotherapy in participants receiving therapy at baseline
- Pregnancy
- Participant is lost to follow-up (defined as a participant who fails to comply with scheduled study visits or contact, who has not actively decided to withdraw from the study, and for whom no alternative contact information is available [this implies that at least two attempts have been made to contact the participant])
- Any center personnel break the randomization code for that participant
- The participant attempts suicide or is at significant risk of suicide (either in the opinion of the investigator or defined as a “yes” to suicidal ideation questions 4 or 5 or answering “yes” to suicidal behavior on the C-SSRS during the study)

The reason and date the participant is withdrawn from the study and further treatment with the IMP will be documented in the electronic case report form (eCRF) (e.g., lost to follow-up, consent withdrawn, incorrect enrollment, AEs, etc.).

If a participant is withdrawn from the study, the PI should attempt to complete all study assessments in [Table 1](#) for the EoS Visit.

Participants who withdraw due to an AE should be followed until resolution of the AE, or the PI or delegated center personnel decides that the AE is stable, and the participant does not need further follow-up. All AEs should be followed up according to Section 8 [ADVERSE EVENTS](#).

If a participant is withdrawn from the study, all data collected until the time of withdrawal will be included in the analyses.

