9.6. Interim Analysis

An interim analysis will be performed after 90 participants have completed the specific week assessments (expected 108 patients enrolled after accounting for 20% dropout). Individuals that had the opportunity to complete their specific week visit, but were lost to follow-up, will also be included in the analysis, however, will not be included in the 90-patient count required for initiation of the interim analysis. The objective of this interim analysis will be to reassess the sample size based on the observed variability and effect sizes. The interim analysis will be conducted as per the main efficacy analysis. Imputation and sensitivity analyses will not be performed. A sample size adjustment may be performed using the promising zone approach as described by Mehta and Pocock which allows the sample size to be adjusted based on an interim analysis only if the data are in a promising zone, i.e., the effect is trending toward success but not strong enough to indicate it will finish successfully without increasing the sample size (Mehta & Pocock, 2000). If the effect is strong (favorable zone) or too weak (unfavorable zone) the trial will be allowed to accumulate participants to the originally planned sample size (188 enrolled). If data are within the promising zone, the sample size will be increased in a stepwise fashion to keep the estimated power of the study between 80 and 90%. This step wise approach to increasing sample size at interim is implemented to avoid the possibility of back-calculating the observed effect size from the sample size increase, although variations in standard deviation and placebo decline rates from historical expectations already make this difficult. For both primary endpoints, a new sample size will be determined independently. This will yield two proposed new sample sizes, one per endpoint. The larger proposed increase will be used.

Additional details will be provided in the SAP which will be finalized prior to conduct of the interim analysis.

At the interim analysis, the safety data will also be reviewed by the DMC.

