4.5 Analysis Sets

With regard to analysis of data, the following analysis sets are defined:

- **Safety Analysis Set (SAF):** All subjects who received at least one dose of the study IMP or Placebo. Individual data will be summarized as treated.
- **Full Analysis Set (FAS):** All patients enrolled (randomized) in the study. Patients will be analyzed as randomized.
- **Per-Protocol Set (PPS):** All subjects in the FAS without any major protocol deviations* as described in Section 10.9 of the Clinical Study Protocol (CSP) and who also satisfy both of the following constraints:
 1. Have at least completed one CGI-S A/A assessment at *Weeks 8-12*
 2. Have at least completed one BPDCL assessment at *Weeks 8-12*Individuals in the PPS population will be analyzed as treated.

*Important violations of eligibility criteria and other deviations from the protocol will be assessed in cooperation with the Sponsor. Important deviations from the protocol may lead to exclusion of a subject from the PPS (See Blinded data review below).

Primary efficacy analysis will be performed using the FAS. Patients will be analyzed as per randomized treatment. Sensitivity and supplementary analyses will be performed in the FAS. Efficacy will also be tested in the PPS analysis will be for descriptive purposes only.

The safety summaries and analyses will be based on SAF. The PPS may be used for additional safety analysis.

Before database lock, protocol deviation and analysis set outputs will be produced and will be sent to Oryzon for review. Analysis Set classifications will be discussed during the Blinded Data Review Meeting to decide which subjects and/or subject data will be excluded from certain analyses. Decisions made regarding the exclusion of subjects and/or subject data from analyses will be made prior to unblinding and will be documented and approved by Oryzon.

A summary of patients (counts and frequencies) in each analysis set, including reasons for exclusion, will be produced in addition to a listing of analysis set assignments by patient, including any reasons for exclusion.

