4.8 Interim Analyses

An interim analysis will be conducted after 90 patients have completed their *Week 10* evaluations (expected 108 patients enrolled after accounting for 20% dropout). Individuals that had the opportunity to complete their Week 10 visit but were lost to follow-up will also be included in the analysis, however, will not be included in the 90-patient count required for interim analysis initiation. In addition, unblinded safety outputs will be produced. After the patient count requirement for interim analysis has been reached, sufficient time will be allowed for data cleaning, data transfers (including laboratory) and medical coding.

The interim analysis will be conducted as per the main efficacy analysis described in Section 5.1.13. Sensitivity analyses will not be performed.

A sample size adjustment will be performed using the promising zone approach as described by Mehta and Pocock ([1]) which allows the sample size to be adjusted based on an interim analysis only if the data are in a promising zone, i.e., the effect is trending toward success but not strong enough to indicate it will finish successfully without increasing the sample size. If the effect is

strong (favorable zone) or too weak (unfavorable zone) the trial will be allowed to accumulate participants to the originally planned sample size (188 enrolled; 150 anticipated completers). If data are within the promising zone, the sample size will be increased in a stepwise fashion to keep the estimated power of the study between 80 and 85%. This step wise approach to increasing sample size at interim is implemented to avoid the possibility of back calculating the observed effect size from the sample size increase, although variations in standard deviation and placebo decline rates from historical expectations already make this difficult.

As Mehta and Pocock assess single outcomes, we interrogated control of the type I error rate using dual outcomes as proposed in this SAP. The code to generate the simulation and results showing that this approach effectively controls type I error in a Promising Zone simulation can be found in the attached document `promising_zone_simulation.R`. Images produced with this code can be found in Appendix 7.2.

[figure not shown]

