At interim analysis two discontinued individuals reached visit 6, and were included in the IA analysis. The table below was adjusted for 92 individuals worth of information, as opposed to the 90 individuals mentioned above.

Table 1. Promising Zone Thresholds

	Test Statistic at Interim	Completers	Sample Size (total Enrollment)
Futility	$-\infty < Z \leq -1.987$	N at time of futility declaration	--
Unfavorable Zone	$-1.987 < Z < 1.412$	150	188
Promising Zone	$1.412 \leq z < 1.555$	300	376
	$1.555 \leq z < 1.649$	265	332
	$1.649 \leq z < 1.745$	231	290
	$1.745 \leq z < 1.845$	201	252
	$1.845 \leq z < 1.944$	174	218
Favorable Zone	$1.944 \leq z < \infty$	150	188

Sample size calculations will be generated as described below. The more conservative sample size calculation between the two primary efficacy endpoints will be used.

The following formulas will be used:

$$CP(z_1, \tilde{n}_2) = 1 - \Phi \left(\frac{z_\alpha \sqrt{n_2} - z_1 \sqrt{n_1}}{\sqrt{\tilde{n}_2}} - \frac{z_1 \sqrt{\tilde{n}_2}}{\sqrt{n_1}} \right)$$

$$\tilde{n}_2' = \left(\frac{n_1}{z_1^2} \right) \left(\frac{z_\alpha \sqrt{n_2} - z_1 \sqrt{n_1}}{\sqrt{n_2} - n_1} + z_\beta \right)^2$$

Here:

- z_1 is the Wald-statistic observed at the interim analysis,

- α is the *one-sided* significance level of the test (here 2.5%),
- z_{α} is the corresponding critical value of the normal distribution,
- n_2 is the total number of patients originally planned,
- \tilde{n}_2 is the incremental number of patients $n_2 - n_1$,
- \tilde{n}_2' is the proposed new incremental number of patients,
- β is 1 - statistical power, and
- Φ is the cumulative density function of the normal distribution.

Note: \tilde{n}_2' will only be calculated if CP is in the promising zone. Both n_2 and the adapted sample size $n_2' = n_1 + \tilde{n}_2'$ are adjusted for the expected drop-out rate, i.e., the n_2 is considered to be 150 and $n_2 / 0.8$ patients (rounded up to an even number) will be recruited after adaptation of the sample size.

If the CP for both endpoints is below 40%, the study will be continued without modifications.

Details for the safety deliverables are described in Section 5.2.11.

All analyses at interim will be conducted by a separate unblinded statistical team.

The decision tree for promising zone can be found in appendix 7.3.

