Sites with less than two study participants per arm will be pooled. To pool sites: sites with less than two study participants per arm will be ranked within country by the number of participants within the placebo arm (higher numbers are ranked higher). Ranked sites will be pooled starting by pooling the highest ranks until the study participant requirement per arm is met. If more sites are present after the pooling criterion is met the remaining sites are pooled to meet the criterion. In the event that remaining sites do not meet the criterion they will be combined with the previously pooled group. In the event of a tie for ranking the sites, the site with the largest number in the active arm will be used. If the tie persists the sites will be ordered alphabetically or numerically (A and higher number result in a higher rank). Due to the small sample size the interim analysis will be ranked across all sites for pooling as opposed to within country.

Pooling at interim will not include country due to the small number of individuals.

The primary treatment contrast will be based on the LS means from the treatment by visit interaction term. A contrast statement will be written such that model estimates from assessments collected between weeks 8-12 are averaged to compare drug vs placebo.

The test will be a two-sided test of the null hypothesis of no difference between active treatment and placebo at *Weeks 8-12*.

A listing by subject of the CGI-S A/A scores including changes from baseline will be provided.

Individuals with no post-baseline information will have the first post-baseline visit imputed. Individuals reported to drop out for lack of efficacy will be given the baseline placebo mean. Individuals reported as dropping out for any other reason will be given the baseline group mean of their corresponding treatment.

Reasons not associated with lack of efficacy include but are not limited to the following:

- Participant Decision Due to COVID
- Lost to Follow-up
- Adverse Event
- Protocol Deviation
- Physician Decision
- Non-Compliance
- Blood Value During Randomization Visit Was Exclusionary
- Withdrawal by Subject

For the primary efficacy analyses all other missing data will be accounted for using the MMRM estimates.

The analysis of Total BPDCL will not include a categorical summary table.

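### The set of participants behind the interim z is described in three ways that do not agree, and two of them, read literally, select on what happened after randomisation

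*Protocol*

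**What the plan says.** **The inclusion sentence.** The Protocol Synopsis (Statistical Methods), 3.1 and 9.6 start the interim once 90 participants have completed the masked visit. They add that "Individuals that had the opportunity to complete their specific week visit, but were lost to follow-up, will also be included in the analysis", without counting toward the 90. SAP 4.8 unmasks the visit: "Individuals that had the opportunity to complete their Week 10 visit but were lost to follow-up will also be included in the analysis".

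**What loss to follow-up means.** Protocol 4.2 describes someone who misses visits or contact, "who has not actively decided to withdraw from the study, and for whom no alternative contact information is available". SAP 5.1.1 lists it as one dropout reason among several. Adverse event, physician decision and "Withdrawal by Subject" are separate entries, and lack of efficacy is handled under its own imputation rule.

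**The reference to the main analysis.** Protocol 9.6 states: "The interim analysis will be conducted as per the main efficacy analysis. Imputation and sensitivity analyses will not be performed". SAP 4.8 also ties the interim to the main efficacy analysis but rules out only sensitivity analyses. The main analysis uses the FAS, which SAP 4.5 defines as "All patients enrolled (randomized) in the study. Patients will be analyzed as randomized". SAP 4.6 has the primary analysis use every available assessment.

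**What was done.** Just above Table 1, SAP 4.8 reports: "At interim analysis two discontinued individuals reached visit 6, and were included in the IA analysis". The Table 1 thresholds were then set for 92 participants' worth of information instead of 90.

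**The concern.** A reader programming the interim dataset cannot tell who belongs in it. Taken literally, the inclusion sentence admits Week 10 completers plus one category of dropout. It does not cover people who stopped for an adverse event, lack of efficacy or active withdrawal, nor someone who missed only Visit 7. The Visit 6 statement selects on a different event, namely staying until Week 8. Each of these conditions on something that happens after randomisation and may depend on treatment. The reference to the main analysis selects on nothing.

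The choice matters because this z does one job: it picks the row of Table 1. If the set behind it is selected, the trial can be enlarged, or left at 150 completers, on a contrast that is not the one the final FAS analysis estimates.

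**Working it through.** **1. The three descriptions side by side**

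| Source | Who enters, read literally | Selects on |
|---|---|---|
| Synopsis, 3.1, 9.6; SAP 4.8 inclusion sentence | Week 10 completers, plus those with the opportunity to complete it who were lost to follow-up | Completion and dropout reason |
| Protocol 9.6 and SAP 4.8, reference to the main analysis (SAP 4.5, 4.6) | All randomised, all available assessments | Nothing |
| SAP 4.8, statement above Table 1 | The 90, plus discontinued participants who reached Visit 6 (Week 8) | Staying to Week 8 |

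The second row does not settle matters alone. Taken literally it would also admit ongoing participants not yet due at Week 10, which conflicts with the opportunity condition. The Synopsis defines the FAS differently (at least one dose and one post-baseline efficacy score). The section number that SAP 4.8 cites for the main analysis, 5.1.13, does not appear in the SAP; the primary analysis is in 5.1.1.

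**2. Reproducing the plan's thresholds**

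SAP 4.8 formula: CP = 1 − Φ[(z_α√n2 − z1√n1)/√(n2 − n1) − z1√(n2 − n1)/√n1], with z_α = 1.960, n2 = 150, n1 = 92.

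- z1 = 1.412: (24.005 − 13.543)/7.616 − 1.121 = 0.2525, so CP = 0.400. The plan states 40%.
- z1 = 1.944: (24.005 − 18.646)/7.616 − 1.544 = −0.840, so CP = 0.7995, the 80% edge of the zone.

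Both bounds reproduce at n1 = 92. At n1 = 90, CP at 1.412 would be 0.414. So n1 is the 90 completers plus the two discontinued participants.

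**3. How many dropouts are in question**

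The plan expects 108 enrolled, hence 108 − 90 = 18 dropouts. At a true 20% it would be 90/0.8 = 112.5, rounded up to 113, hence 23; 108 is 90 × 1.2, which implies 16.7% dropout. Beyond the two counted in n1, that leaves 108 − 92 = 16 to 113 − 92 = 21.

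**4. How finely Table 1 is cut**

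Promising-zone bin widths in z: 1.555 − 1.412 = 0.143, then 0.094, 0.096, 0.100 and 0.099. A shift of about 0.1 can therefore change the completer target.

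**5. Illustration only**

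Assume m = 16 or 21 dropouts are wholly absent from a z based on 92, that adding them gives each full weight, that arms are balanced with equal SD, and that they show a fraction f of the effect in the 92. Then z′ = z(92 + fm)/√[92(92 + m)]. Completer targets are read from Table 1 as it stands.

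| z on 92 (target) | f = 0 | f = 0.5 | f = 1 |
|---|---|---|---|
| 1.45 (300) | 1.34 to 1.31 (150) | 1.46 (300) | 1.57 to 1.61 (265) |
| 1.80 (201) | 1.66 to 1.62 (231 to 265) | 1.81 (201) | 1.95 to 2.00 (150) |
| 2.00 (150) | 1.85 to 1.81 (174 to 201) | 2.01 (150) | 2.17 to 2.22 (150) |

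The sign depends wholly on f, which the documents do not give. Full weight is an upper extreme, since a participant with only early visits contributes less to a Weeks 8–12 contrast.

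**6. n1 moves the thresholds too**

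With n1 = 108 or 113 in the same formula, the 40% bound becomes 1.549 or 1.592, not 1.412. How dropouts are counted in n1 therefore needs a rule as well.

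**The case against.** The inclusion sentence adds people and contains no word restricting the set to them. It sits beside the 90-participant trigger and can be read as a rule about that count. The set itself is arguably fixed elsewhere: the interim follows the main analysis, that analysis takes all randomised participants with all available data, and Protocol 4.2 keeps a withdrawn participant's data up to withdrawal. SAP 5.1.1 lists the other dropout reasons because those people are in the primary analysis. The participants added above Table 1 are called discontinued, which suggests the narrow term was not applied strictly. The Visit 6 condition may serve only to count who informs a Weeks 8–12 average. The final test uses the FAS in any case.

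Most of this stands, and it bars a stronger inference that a reader might draw: that dropouts for adverse events, lack of efficacy or withdrawal were left out of the interim z. No text excludes them. The gap between two dropouts mentioned and roughly 18 to 23 expected shows only that the others were not counted as information in n1. It does not show that their early-visit data were missing from the model.

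What the objection does not remove is the conflict. If every dropout were already in, the additive sentence would have no work to do. SAP 4.8 says the two participants were included in the analysis, not merely counted.

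**Conclusion.** The interim analysis set is described inconsistently. Two of the three descriptions, followed as written, give a set selected on post-randomisation dropout for a statistic that chooses between 150 and 300 completers. That is more than missing detail, because a programmer obeying the explicit inclusion sentence would build the selected set.

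The size cannot be fixed. The documents give no interim dropout by reason or arm, so neither the direction nor the amount of any bias in z can be determined. The table in the working shows what could happen if 16 to 21 participants were wholly absent and carried full weight; it is not an estimate of what did happen. The finding concerns the sample-size decision. Nothing here shows a Type I error problem or a fault in the final FAS estimate. It should be corrected; the cost is small.

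**What to change.** Replace the loss-to-follow-up clause in the Synopsis, 3.1, 9.6 and SAP 4.8 with one rule:

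*Every randomised participant (FAS as in SAP 4.5) whose Week 10 window has closed by the data cut-off is included with all available assessments, whether or not Week 10 was attended and whatever the reason for discontinuation. Only Week 10 completers count toward the 90.*

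In the blinded protocol sections, keep the masked visit name.

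In addition:
- State how participants without Week 10 data enter n1 in the conditional power formula, and whether reaching Visit 6 affects only that count.
- Reconcile Protocol 9.6, which bars imputation at the interim, with SAP 4.8, which does not, and SAP 5.1.1, which imputes a first visit for participants with no post-baseline data.
- Correct the section reference in SAP 4.8 and align the Synopsis FAS definition with SAP 4.5.
- Because SAP 4.8 describes the interim in the past tense, document which set was analysed. If it was narrower than this rule, report the interim z on the full set.

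The cost is a few sentences and one dataset filter, with at most one re-run on data already collected. No extra participants or visits are needed.
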